- c. For the time that the consent form is signed until treatment allocation/randomization, any events of clinical interest (ECI, refer to 6.2.3.2), serious adverse event, or follow up to a serious adverse event, including death due to any cause other than progression of the cancer under study (reference Section 6.2.3.3 for additional details) that occurs to any patient must be reported within 24 hours to the Sponsor. AEs will continue to be assessed and reported throughout the trial treatment period, for 30 days following the EOT and again at 90 days for serious adverse events (refer to Section 6.2 for complete details).
- d. Complete physical exam at screening including height and weight, directed physical exam with weight for day 1, 8, 15 of each cycle and at the EOT.
- e. Vital signs to include: Blood pressure, pulse, respiratory rate, and temperature.
- f. ECOG Performance Status must be 0 or 1 to be eligible for entry to the trial.
- g. Negative serum pregnancy test is required for women of child-bearing potential (WOCBP) within 24 hours of start of trial medication. Pregnancy testing will be performed whenever an expected menstrual cycle is missed or when pregnancy is otherwise suspected. Participants must agree to use a contraception as detailed in Section 4.7.2
- h. Refer to Table 9 for details of required labs to be included. Adequate organ function must be demonstrated in accordance with protocol criteria within 10 days of start of trial medication as defined in Table 2.
- i. TSH, T3, Free T4, and PTH (not required at C1/Day 1 if completed at SCN within 21 days). Results must be reviewed prior to treatment initiation. Repeated every other cycle throughout treatment period (i.e. prior to Cycle 3, 5, 7, etc.).

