6.1.2.6 Tumor Imaging and Assessment of Disease

The patient's pancreatic cancer will be evaluated by the investigator based on tumor assessments using RECIST 1.1 and iRECIST criteria (Appendix 5).

Tumor assessments for evaluation of response will be conducted using CT or MRI, approximately every 9 ± 1 weeks until trial discontinuation or disease progression, whichever is later. All sites of disease must be followed using the same baseline assessment method.

CT is the preferred imaging modality for this study. I.V. contrast should be administered, unless medically contraindicated.

If CT with I.V. contrast is contraindicated, the alternative is to acquire a CT of the chest without contrast and MRI of the abdomen and pelvis with gadolinium contrast.

Other protocols, such as non-contrast CT of chest abdomen pelvis, should not be performed. For CT scans oral contrast should be administered in addition to IV contrast. Radiolucent agents (e.g., water) are generally preferred over radiopaque agents (e.g., iodine and barium-based agents).

All target lesions will be measured by consistent imaging techniques for each patient throughout the trial. Suitable imaging techniques include CT-scan, or MRI. The same technique should be used for each evaluation in an individual patient. Copies of the scans must be available for review.

In addition, a central radiologist, blinded to the treatment assignment, will perform an independent read of each scan, assessing tumor response using RECIST 1.1 and iRECIST criteria (Appendix 5).

In the event that PD by RECIST 1.1 or iUPD is determined, a repeat scan must be performed within 4 - 6 weeks to confirm PD. Trial treatment may be continued during this time (past the initial PD assessment) but only if patient is clinically stable as defined by:

- No worsening of performance status

- No clinically relevant increase in disease related symptoms
- No requirement for intensified management of disease related symptoms (analgesics, radiation, palliative care)

If the investigator assesses a patient to have PD (defined by RECIST 1.1), the central radiologist will review the scan to confirm the PD, prior to the discontinuation of trial treatment.

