CA19-9 assessments (or CEA or CA-125 for not expressers of CA19-9) will be taken at baseline and approximately every 21 days during the trial treatment period. All CA19-9 assessments must be assayed by the same laboratory for each patient. Disease progression will not be determined by CA19-9, however increases in CA19-9 may warrant the investigator to obtain radiographic assessments.

Note: In order to more precisely determine time to progression, the investigator is encouraged to obtain radiological assessments and CA19-9 values earlier if there is a strong clinical suspicion of disease progression. In order to either confirm or refute the clinical impression.

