6.1.7.3 End of Treatment (EOT)

The patient will continue on maintenance therapy until there is evidence of clear-cut tumor progression, has treatment ending toxicities, or withdraws from treatment (refer to section 4.8). The following assessments will be performed within 5 days after completing the last dose of trial medication or before the initiation of a new anti-cancer treatment, whichever comes first:

- Directed physical exam
- ECOG Performance Status (see Appendix 4)
- Vital signs
- ECG
- Hematology: CBC with differential and platelet count
- Serum chemistries
- TSH, T3, T4
- CA19-9 (or CEA or CA-125 if not expressers of CA19-9)
- Urinalysis
- Serum β -HCG pregnancy test (for WOCBP)
- Central lab blood sample, 2 X10 mL vials
- Concomitant medication
- Patient to complete the PPCB App (Appendix 6)

- Provide Fecal Swab collection kit and review instructions (Appendix 9) with patient for return of sample within 72 hours of collection (coordinate with 30 day Safety Follow-Up visit)
- CT/MRI scan to evaluate disease status (using same imaging method as Baseline). Obtain De-identified dicomm encoded CT scan for central lab (Appendix 7).
- AEs using the NCI CTCAE Version 4.0 (see Appendix 3)
- Review contraception use as required by protocol Section 4.7.2 (where applicable)
- Confirm contact information for patient and a designated family member and remind patient of FU telephone contact that will be conducted every 90 days for survival status following the 30 - day follow-up visit.

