6.2 Assessing and Recording Adverse Events

An adverse event is defined as any untoward medical occurrence in a patient or clinical investigation patient administered a pharmaceutical product and which does not necessarily have to have a causal relationship with this treatment. An adverse event can therefore be any unfavorable and unintended sign (including an abnormal laboratory finding, for example), symptom, or disease temporally associated with the use of a medicinal product or protocol-specified procedure, whether or not considered related to the medicinal product or protocol-specified procedure. Any worsening (i.e., any clinically significant adverse change in frequency and/or intensity) of a preexisting condition that is temporally associated with the use of the pembrolizumab and /or paricalcitol, is also an adverse event.

Adverse events may occur during the course of the use of pembrolizumab and/or paricalcitol in clinical trials, or as prescribed in clinical practice, from overdose (whether accidental or intentional), from abuse and from withdrawal.

Progression of the cancer under study (pancreatic cancer) is not considered an adverse event.

All adverse events that occur after the consent form is signed but before treatment allocation/randomization must be reported by the investigator if they cause the patient to be excluded from the trial, or are the result of a protocol-specified intervention, including but not limited to washout or discontinuation of usual therapy, diet, placebo treatment or a procedure.

From the time of treatment allocation/randomization through 30 days following cessation of treatment, all adverse events must be reported by the investigator. Such events will be recorded at each examination on the Adverse Event case report forms/worksheets. The reporting timeframe for adverse events meeting any serious criteria is described in section 6.2.3.1. The investigator will make every attempt to follow all patients with non-serious adverse events for outcome.

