For the time period beginning at treatment allocation/randomization through 90 days following cessation of treatment, or 30 days following cessation of treatment if the patient initiates new anticancer therapy, whichever is earlier, any serious adverse event, or follow up to a serious adverse event, including death due to any cause other than progression of the cancer under study (reference Section 6.2.3.3 for additional details), whether or not related to the trial treatment, must be reported within 24 hours to the Sponsor. The Sponsor will report within 24 hours (working days) to Merck Global Safety.

Additionally, any serious adverse event, considered by an investigator who is a qualified physician to be related to pembrolizumab that is brought to the attention of the investigator at any time following consent through the end of the specified safety follow-up period specified in the paragraph above, or at any time outside of the time period specified in the previous paragraph also must be reported immediately to the Sponsor. The Sponsor will then report to Merck Global Safety.

All patients with serious adverse events must be followed up for outcome.

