6.2.4 Evaluating Adverse Events

AE Grade

An investigator who is a qualified physician will evaluate all adverse events according to the NCI Common Terminology for Adverse Events (CTCAE), version 4.0. A copy of the CTCAE Version 4.0 can be downloaded from the CTEP website at: https://ctep.cancer.gov/protocoldevelopment/electronic_applications/ctc.htm

Any adverse event which changes CTCAE grade over the course of a given episode will have each change of grade recorded on the adverse event case report forms/worksheets.

When specific adverse events are not listed in the CTCAE they will be graded by the investigator according to the following grades and definitions, consistent with the CTCAE Version 4.0.

- Grade 1: Mild; asymptomatic or mild symptoms; clinical or diagnostic observations only; intervention not indicated.
- Grade 2: Moderate; minimal, local or noninvasive intervention indicated; limiting age-appropriate instrumental activities of daily living (ADL). Instrumental ADL refer to

preparing meals, shopping for groceries or clothes, using the telephone, managing money, etc.

- Grade 3: Severe or medically significant but not immediately life-threatening; hospitalization or prolongation of hospitalization indicated; disabling; limiting self care ADL. Self care ADL refer to bathing, dressing and undressing, feeding self, using the toilet, taking medications, and not bedridden
- Grade 4: Life-threatening consequences; urgent intervention indicated.
- Grade 5: Death related to AE.

Duration

The investigator will record the start and stop dates of the adverse event. If less than 1 day, this will be indicated in the appropriate length of time in units.

Action Taken

Did the adverse event cause the trial treatment to be discontinued?

Relationship

All adverse events regardless of CTCAE grade must also be evaluated for relationship (in regards to trial treatment/ trial interventions).

The determination of the likelihood that trial treatment caused the adverse event will be provided by an investigator who is a qualified physician. The investigator's signed/dated initials on the source document or worksheet that supports the causality noted on the AE form, ensures that a medically qualified assessment of causality was done. This initialed document must be retained for the required regulatory time frame.

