| PR | Non-PD/ not all evaluated | No | PR | Documented at least once ≥4 wks. from baseline |
| SD | Non-PD/ not all evaluated | No | SD | |
| Not all evaluated | Non-PD | No | NE | |
| PD | Any | Any | PD | |
| Any | PD | Any | PD | |
| Any | Any | Yes | PD | |
| Non target lesions ONLY | | | | |
| No Target | CR | No | CR | Normalization of tumour markers, tumour nodes <10 mm |
| No Target | Non-CR/non-PD | No | Non-CR/non-PD | |
| No Target | Not all evaluated | No | NE | |
| No Target | Unequivocal PD | Any | PD | |
| No Target | Any | Yes* | PD | |
| 
Note: Patients with a global deterioration of health status requiring discontinuation of treatment without objective evidence of disease progression at that time should be reported as “symptomatic deterioration”. This is a reason for stopping therapy, but is NOT objective PD. Every effort should be made to document the objective progression even after discontinuation of treatment.
 
*Investigators should record all new lesions; if the new lesion is felt to be equivocal, treatment may be continued pending further assessments – see table 2.
 | | | | |

3. iRECIST Response Assessment

Overall response will also be assessed using iRECIST. Immunotherapeutics may result in infiltration of immune cells leading to transient increase in the size in malignant lesions, or undetectable lesions becoming detectable. The criteria are identical to those

of RECIST 1.1 in many respects but have been adapted to account for instances where an increase in tumour burden, or the appearance of new lesions, does not reflect true tumour progression.

Key differences are described below. All responses defined using iRECIST criteria are designated with a prefix. iRECIST time-point and best overall responses will be recorded separately.

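### From randomization on, a death attributed to progression is exempt from SAE reporting with no imaging standard, so an unimaged death on treatment can be missing from the safety tables

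*Protocol*

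**What the plan says.** Protocol 6.2.3.1 sets out two reporting periods. The one that matters here starts at randomization and ends 90 days after treatment stops, or 30 days after if new anticancer therapy starts first. In that period any serious adverse event goes to the sponsor within 24 hours, "including death due to any cause other than progression of the cancer under study (reference Section 6.2.3.3 for additional details". The text then runs from 6.2.3.2 straight to 6.2.4, so there is no Section 6.2.3.3.

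Section 6.2 adds: "Progression of the cancer under study (pancreatic cancer) is not considered an adverse event". Causality is assessed under 6.2.4, which is limited to adverse events: "All adverse events regardless of CTCAE grade must also be evaluated for relationship".

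On imaging, 6.1.2.6 has tumor assessments "conducted using CT or MRI, approximately every 9 ± 1 weeks". Between those, the investigator is "encouraged to obtain radiological assessments and CA19-9 values earlier if there is a strong clinical suspicion of disease progression". At the end of treatment, 6.1.7.3 includes a CT or MRI and says: "The following assessments will be performed within 5 days after completing the last dose of trial medication". Appendix 5 states that clinical deterioration without objective evidence does not count as objective progression, and adds: "Every effort should be made to document the objective progression even after discontinuation of treatment".

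Protocol 8.3.5.1 lists and tabulates adverse events, SAEs and events of clinical interest. SAP Table 3 has a row for adverse events that led to death and a row for SAEs. It has no row for deaths from all causes.

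**The concern.** Early deaths on a new combination are what a safety review most needs to see. Protocol 4.2.4 says that immune-related events can begin soon after the first pembrolizumab dose, and 4.6.1 tells the investigator to rule out metastatic disease as another explanation. The protocol thus accepts that toxicity and progression can look alike at the bedside.

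If such a patient dies without a scan and the death is called progression, nothing in the reporting rule tests that label. The death is then neither an adverse event nor an SAE. It receives no relationship assessment of its own and does not enter the safety tables. The protocol is stricter on a lesser decision: under 6.1.2.6, central radiology reviews an investigator's call of progression before treatment is stopped.

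**Working it through.** The plan gives no figure on this point to reproduce. The check is mainly a reading of the rules, followed by scale calculations.

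**1. Route of an unimaged death labelled progression, after randomization**
- SAE report (6.2.3.1): exempt, with no evidence standard stated.
- Adverse event (6.2): no, because progression is not one.
- Relationship assessment (6.2.4): not required, because it applies to adverse events.
- SAE listing (8.3.5.1) and the fatal-event row (SAP Table 3): absent.
- Overall survival (Protocol 8.3.5.2, SAP 7.1): counted as an event.

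**2. Which scans could verify the label**
The routine scan, the encouraged early scan, the end-of-treatment scan and the central read all need a living patient. Many patients who stop treatment will have one. A patient who dies on treatment, or before an end-of-treatment or unscheduled scan, may have no image for central radiology to check.

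**3. Exposure before the first routine scan**
Week 9 ± 1 is day 56 to day 70.
- Pembrolizumab: days 1, 22 and 43 give 3 doses by day 56; day 64 makes 4 by day 70.
- Paricalcitol or placebo, nine per 21-day cycle: 9 + 9 + 6 = 24 by day 56; 27 + 3 (days 64, 66, 68) = 30 by day 70.

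This shows that real exposure can precede any routine image. It says nothing about how often a death occurs.

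**4. Weight of one death**
1/12 = 8.3 percentage points of an arm. As an illustration with assumed counts, take a true 3/12 against 0/12 fatal adverse events. Pearson chi-squared = 24 × (3×12 − 0×9)² / (12×12×3×21) = 3.43, two-sided p = 0.064. With one of the three labelled progression the table shows 2/12 against 0/12: 24 × (2×12 − 0×10)² / (12×12×2×22) = 2.18, p = 0.140.

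**5. How many deaths the rule could touch**
The documents give no rate. Let p be an assumed per-patient risk of an unimaged death labelled progression, rightly or wrongly, with n = 24. Expected number = 24p; chance of at least one = 1 − (1 − p)^24.

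| Assumed p | Expected | At least one |
|---|---|---|
| 2% | 0.48 | 38% |
| 5% | 1.2 | 71% |
| 10% | 2.4 | 92% |

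**The case against.** The strongest reply is that a toxic death rarely leaves no trace. Adverse events are assessed at each paricalcitol or placebo visit, three times a week, with examination and laboratory tests weekly. All adverse events from randomization to 30 days after treatment are recorded, graded and assessed for relationship. Hospitalization for an adverse event is itself an SAE. A toxic death vanishes from the safety data only if no preceding event was recorded, or if every preceding event was also called progression. This stands, and it makes the gap small.

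Exempting progression deaths is also a reasonable choice in stage IV pancreatic cancer. That stands too: the defect is the missing evidence rule, not the exemption.

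Several stronger readings are tempting but unsupported.
- A reader might infer that the same wording elsewhere widens the problem. Table 7 footnote c ("including death due to any cause other than progression of the cancer under study") and the first reporting period in 6.2.3.1 cover consent to randomization. Those patients have had no trial drug, and 8.3.5.1 starts at Cycle 1 Day 1.
- A reader might take 38%, 71% and 92% as the chance of losing a toxic death. They are the chance of any unimaged death labelled progression, under assumed risks, and many such labels will be correct.
- A reader might infer that the medical monitor never sees these deaths. Section 9.8.2 gives that person an unblinded report without saying whether it lists all deaths. The Data Safety Monitoring Plan was not supplied and may require it.
- A reader might infer that efficacy is affected. A death labelled progression is an event in the Kaplan-Meier and log-rank analyses of survival. The Fine and Gray analyses in SAP 7.1 do divide deaths by cause, but this point is confined to safety data.

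**Conclusion.** The concern holds in a limited form. As written, 6.2.3.1 lets an unimaged death after randomization leave the SAE listings and the fatal-event row of SAP Table 3 on the investigator's label, without a causality assessment of the death itself. The section cited for details is missing, and Table 3 has no all-cause row that would reveal the omission.

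Severity is low to moderate. One death is 8.3 points of an arm of 12, but the number of mislabelled deaths cannot be estimated from the documents. The conclusion rests on the protocol and SAP alone; the Data Safety Monitoring Plan could close the oversight part of the gap. It is worth correcting because the change is cheap and the combination is new.

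**What to change.** Change the reporting period in 6.2.3.1 that begins at randomization, and leave the pre-randomization rule and Table 7 footnote c as they are. Suggested text:

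'A death in this window is exempt only if RECIST 1.1 progression was documented on imaging before death and the investigator judges progression to be the cause. Any other death is reported to the Sponsor in the same timeframe as an SAE, with the attributed cause (including suspected progression, not imaged) and a relationship assessment, notwithstanding the statement in 6.2 that progression is not an adverse event.'

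Both conditions are needed. Under 6.1.2.6 a clinically stable patient may stay on treatment after a first progression call, so imaged progression alone does not settle the cause of death.

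Delete the reference to 6.2.3.3. In SAP Table 3 add a row by arm for all deaths within the SAE reporting window, split into fatal adverse event, documented progression, and suspected progression not imaged. The existing fatal-event row then does not absorb cancer deaths, and the unverified ones become visible. If the Data Safety Monitoring Plan does not already require it, list all deaths by arm, with attributed cause and days from first dose, in the independent medical monitor's unblinded report.

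Cost: a few sentences, one split row, and about 0.5 to 2.4 extra expedited reports in 24 patients at the assumed risks of 2% to 10%. Some will be genuine cancer deaths, which the separate category keeps apart. Deaths already recorded should be checked against the new rule, since the note to SAP Table 3 shows that safety reporting was under way by November 2019. The medical monitor, who already receives unblinded reports, would see deaths by arm in a trial with no planned interim analysis; the trial team stays blinded. No new scan or reader is needed.

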6.2.3.2 Events of Clinical Interest (ECI)

Selected non-serious and serious adverse events are also known as Events of Clinical Interest (ECI) and must be reported within 24 hours to the Sponsor and the Sponsor will report within 24 hours (working days) to Merck Global Safety.

Events of clinical interest for this trial include:

1. An overdose of pembrolizumab, as defined in Pharmacy manual and Section 6.2.1 - Definition of an Overdose for This Protocol and Reporting of Overdose, that is not associated with clinical symptoms or abnormal laboratory results.
2. An elevated AST or ALT lab value that is greater than or equal to 3X the upper limit of normal and an elevated total bilirubin lab value that is greater than or equal to 2X the upper limit of normal and, at the same time, an alkaline phosphatase lab value that is less than 2X the upper limit of normal, as determined by way of protocol-specified laboratory testing or unscheduled laboratory testing. *

*Note: These criteria are based upon available regulatory guidance documents. The purpose of the criteria is to specify a threshold of abnormal hepatic tests that may require an additional evaluation for an underlying etiology.

For the time period beginning when the consent form is signed until treatment allocation/randomization, any ECI, or follow up to an ECI, that occurs to any patient must be reported within 24 hours to the Sponsor and the Sponsor will report within 24 hours (working days) to Merck Global Safety if it causes the patient to be excluded from the trial, or is the result of a protocol-specified intervention, including but not limited to washout or discontinuation of usual therapy, diet, placebo treatment or a procedure.

For the time period beginning at treatment allocation/randomization through 90 days following cessation of treatment, or 30 days following cessation of treatment if the patient initiates new anticancer therapy, whichever is earlier, any ECI, or follow up to an ECI, whether or not related to pembrolizumab, must be reported within 24 hours to the Sponsor and the Sponsor will report within 24 hours (working days) to Merck Global Safety.

